9.2 Setting and Study Population

The study population includes pregnant women with ASCVD, or **hypercholesterolemia associated with** FH exposed to evolocumab during pregnancy when used to treat hypercholesterolemia, and 2 matching comparison groups (1 disease-matched group of women without exposure to evolocumab, and 1 non-disease-matched group of women without exposure to evolocumab nor to any known human teratogen during pregnancy) who reside in the US or Canada.

OTIS member services receive over 70,000 teratogen information telephone inquiries per year, OTIS members constitute a major, but not the only, source of identification and recruitment of exposed women and appropriate comparison women

([Chambers et al, 2001](#)). Once women are in contact with the Registry Coordinating Center, enrollment in the Registry is voluntary and requires informed consent of the pregnant woman. The Registry encourages enrollment as early in the pregnancy as possible, before any prenatal testing results are known.

Although the Registry will follow up on all pregnancies exposed to evolocumab, the core of the Registry will be a prospective cohort study designed to ascertain and follow-up on pregnancy exposures to evolocumab and to compare these to 2 internally-generated comparison groups (Comparison Groups I and II) and 1 external comparison group (MACDP). Participating centers will be MotherToBaby Teratology Information Services or individuals who are members of OTIS in North America and who agree to the study protocol as established by the OTIS Research Committee and described herein.

9.2.1 Study Period

The study **started when the** first subject enrolled (FSE) in **December** 2016, and is **anticipated to** end in October 2030, with a final report submitted to the FDA in April 2031.

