9.2.2 Subject Enrollment

Subject recruitment will continue for 10 years, even if the expected sample size of 75 exposed pregnancies is reached at an earlier time point. If after 10 years the minimum sample size of 75/150 is not reached, enrollment will cease with the FDA's agreement.

Spontaneous referrals from MotherToBaby/OTIS member services and sites will be a source of recruitment for the Registry. MotherToBaby/OTIS Pregnancy Studies have utilized repeated direct mailing campaigns to provide information to health care

professionals who are likely to treat women with the underlying conditions of interest, and this strategy will be continued with the Registry. Registry staff will participate in scientific meetings of professional organizations to initiate and maintain relationships that have been established with referring physicians. In addition, members of the Advisory Board will be asked to promote recruitment among colleagues. The existing Toll Free number for North American callers currently being utilized by all MotherToBaby Pregnancy Studies [contact]) will be maintained and **has been** included in the product label for evolocumab.

The existing MotherToBaby/OTIS Pregnancy Studies contact and referral information is available on the web site and multiple methods are used to increase awareness through the website, social media, and print advertising. The FDA website lists the MotherToBaby/OTIS Pregnancy Studies including this Registry. The study **is** also listed on ClinicalTrials.gov. Additional venues for publicizing the Registry include advocacy groups and patient support networks for FH, and others such as Patients Like Me, BabyCenter.com, pharmacy groups, and professional practice organizations.

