9.2.6 Study Follow-up

Subjects will be enrolled on an ongoing basis through year 10 of the study and each will be followed from the time they enroll, through the 5-year postnatal follow-up period, for an overall study period of 15 years. Pediatric records will be requested 0-6 weeks after delivery and then on an annual basis. Subjects will be considered lost to follow-up if they have completed the initial intake interview but subsequently fail to complete the outcome interview despite repeated attempts within 1 year of the mother's estimated due date. Voluntary subject withdrawals will be considered separately.

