9.5 Study Size

An enrollment total of 75 in the exposed group and 150 in each of the 2 comparison groups after 10 years is anticipated. Given that these numbers assume the prevalence of exposure is sufficient to support recruitment of these numbers, the feasibility of achievement will be re-evaluated at each annual interim review of the data.

Based on previous experience with MotherToBaby/OTIS Pregnancy Studies, we estimate that subjects will be an average of 7-10 weeks post-LMP at the time of enrollment. Given this mean gestational timing at enrollment, the anticipated spontaneous abortion/stillbirth rate is 10%, the estimated elective abortion rate is 5%, and the estimated lost to follow-up rate is 5%. This results in an estimated 71 observable pregnancies of which 60 are estimated to result in live births in cohort 1 (exposed group), and an estimated 142 observable pregnancies of which 120 are estimated to result in live births in cohorts 2 and 3 (control groups).

Baseline rates of major structural **birth** defects, spontaneous abortion, premature delivery, and small for gestational age, as well as the standard deviation for mean birth weight of full-term infants were based on previous MotherToBaby/OTIS studies and on general population data (Table 3). With the sample size estimated above, at $\geq 80\%$ power, alpha of 0.05, two-tailed tests of significance (except as noted below for pattern of minor structural **birth** defects), and each comparison group independently compared to the exposed group, the minimum effect sizes detailed in Table 3 will be detectable.

With respect to the evaluation of minor malformations, the strength of this study design is in the ability to examine the data for a pattern of minor and/or major structural **birth** defects, given that the known human teratogens are typically associated with a pattern as opposed to isolated major **structural** birth defects. A baseline prevalence estimate of 1% has been used for a specific pattern of minor **structural birth** defects. The RR detectable with this sample size is 10.0. This represents a 10% birth prevalence of a specific pattern (ie, approximately 6 children in the exposed sample), which is comparable to the birth prevalence of a specific pattern in other known human teratogens of moderate risk such as the anticonvulsant medications.

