9.7.1.3 Final Analysis

The final analysis will be conducted at the end of the study observation period (currently scheduled to occur 15 years after study commencement) or when the study is determined to have been completed based on other criteria (eg, FDA agreement).

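### The October 2030 end date cannot hold ten years of recruitment plus five years of follow-up for every child, and the stated 15 years matches neither

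*Protocol*

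**What the plan says.** The protocol gives its timeline in several places.

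- **Calendar dates.** Section 9.2.1 places the "first subject enrolled (FSE) in December 2016" and expects the study to "end in October 2030, with a final report submitted to the FDA in April 2031". The milestone table in Section 6 repeats October 2030 for completion and April 2031 for the final report, and gives November 2016 as the start of data collection.
- **Recruitment.** Section 9.2.2: "Subject recruitment will continue for 10 years, even if the expected sample size of 75 exposed pregnancies is reached" early. Section 9.2.6 agrees: "Subjects will be enrolled on an ongoing basis through year 10 of the study".
- **Follow-up.** Section 9.2.6 follows each subject "through the 5-year postnatal follow-up period, for an overall study period of 15 years". The abstract (Section 4) says the same twice.
- **Final analysis.** Section 9.7.1.3 describes it as "currently scheduled to occur 15 years after study commencement", or when the study is judged complete on other criteria, with FDA agreement as the example.
- **Timing of enrollment.** Section 9.5 expects that "subjects will be an average of 7-10 weeks post-LMP at the time of enrollment".

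**The concern.** The calendar dates and the stated durations describe different studies. A reader who plans from the dates closes the study before late-enrolled children turn five. A reader who plans from the durations runs the final analysis after the final report is due.

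Five-year follow-up is part of the purpose. Section 7 gives the FDA requirement as outcomes in live born offspring through the first five years of life, and Section 9.2.3.1 requires women in the three cohorts to agree to five years of follow-up. Section 9.3.2.2.2 defines serious infections, hospitalizations and vaccine reactions over that period, and Section 9.3.2.1 describes separately the defects found between 12 months and five years. These are the outcomes that a closure in October 2030 would shorten.

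**Working it through.** **Inputs.** Start December 2016, end October 2030, report April 2031 (Sections 6 and 9.2.1); 10 years of recruitment (9.2.2); 5 postnatal years per subject and 15 years overall (9.2.6); enrollment at 7-10 weeks on average, and 60 exposed and 120 live births per comparison group expected (9.5). Assumed: a 40-week term, so 30-33 weeks from enrollment to delivery, and uniform accrual for the shares below. Ranges cover any day in the stated months.

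**1. The stated 15 years.**
- 1 December 2016 to 31 October 2030 = 13.9 years; 31 December 2016 to 1 October 2030 = 13.7 years.
- Counting from 1 November 2016 gives at most 14.0 years.
- The stated figure is not reproduced. Fifteen years from December 2016 is December 2031, 8 months after the April 2031 report.

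**2. When the last child turns five.**
- Last enrollment: December 2016 + 10 years = December 2026.
- Last birth: 1 December 2026 + 30 weeks = 29 June 2027; 31 December 2026 + 33 weeks = 19 August 2027.
- Last fifth birthday: 29 June to 19 August 2032.
- Total span: 10 + 0.6 + 5 = 15.6 years. The 10 + 5 sum leaves out 30-33 weeks of gestation, about 7 months.
- Floor: a woman enrolled just before delivery at the close of year 10 has a child who turns five in about December 2031, at least 13 months after closure.

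**3. Who is cut short if October 2030 is kept.**
- Latest birth that reaches age five: October 2030 - 5 years = October 2025.
- Latest matching enrollment: October 2025 - 30 to 33 weeks = about 12 February to 4 April 2025.
- Enrollment after that: 19.9 to 22.6 months of 120, or 16.6% to 18.8%.
- Exposed live births: 60 × 0.166 = 10.0 to 60 × 0.188 = 11.3. Each comparison group: 120 × 0.166 = 19.9 to 120 × 0.188 = 22.6.
- Age of the last child at closure: 3.1 to 3.3 years, or 3.4 if ten years are counted from November 2016.

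**4. Child-time lost.** An affected child loses on average half of the 19.9-22.6 months. Averaged over all children:
- 0.166 × 19.9 / 2 = 1.65 months, or 1.65 / 60 = 2.8% of planned five-year child-time;
- 0.188 × 22.6 / 2 = 2.12 months, or 3.5%.

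**5. Phase II testing (from 3.5 years, Section 9.4.5.2).** October 2030 - 3.5 years = April 2027. Only later births miss the window entirely. These come from about the last 2-5 months of enrollment, and testing stops at 40 per group.

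**The case against.** The best defence is that October 2030 is a forecast. Section 9.2.1 words it as anticipated, the abstract and Section 9.2.6 commit to five years for each subject, and Section 9.7.1.3 allows completion on other criteria. No section orders follow-up to stop in October 2030. This stands: the truncation is conditional on keeping that date. It does not remove the contradiction, because Section 6 lists October 2030 as the planned completion and no section describes an agreement to shorten follow-up.

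It is also fair that the harm is limited. The primary outcome closes at one year of age. Pregnancy and birth outcomes, the tetanus test and the questionnaires at 16 to under 18 months are complete well before October 2030.

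A reader might infer more than the documents support:

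- **That the study cannot deliver its five-year outcomes.** Even with closure in October 2030, roughly 96-97% of planned child-time remains under uniform accrual.
- **That Phase II fails.** Only the latest births miss it, and 40 per group are needed from 60 exposed and 120 comparison live births per group.
- **That unobserved years would be counted as event-free.** No section plans this. Section 9.7.2.4.1 limits the infection subset to infants followed up to one year, which itself sits badly with the five-year definition in Section 9.3.2.2.2, and the handling of unequal follow-up can be left to the SAP.
- **That cohorts recruited at different times would be compared with bias.** No section predicts different accrual.
- **That the affected share is nearer 31%.** That needs linearly rising accrual, and the protocol states no accrual pattern.

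**Conclusion.** The timeline contradicts itself. The dates span about 13.9 years, the text says 15, and the protocol's own rules need about 15.6. The final report is dated 8 months before the 15-year point set for the final analysis. No choice of start day, end day or gestation at enrollment closes the gap.

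If October 2030 is enforced, about 17-19% of subjects lack complete five-year follow-up for serious infections, hospitalizations, vaccine reactions and later-identified defects. Those shares rest on uniform accrual and a 40-week term. The contradiction depends on neither, since the floor of 13 months holds for enrollment just before delivery. The point is a correction of dates and of the number of children with full five-year data. It does not touch the primary outcome or its power.

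**What to change.** Reconcile the abstract (Section 4), the milestones (Section 6) and Sections 9.2.1, 9.2.2, 9.2.6 and 9.7.1.3. There are two ways.

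1. **Move the end date.** Set study completion at the last expected delivery plus five years, about the third quarter of 2032, with the report about six months later, the interval the protocol already uses. Correct the 15 years to include gestation. Administrative truncation then disappears, and no special analysis is needed for it. This needs FDA agreement and a longer study.
2. **Keep October 2030, if it is fixed with FDA.** Correct the 15 years, state that only births through October 2025 contribute complete five-year data, and analyse the five-year outcomes by child-time with administrative censoring at closure. This is mainly wording; the cost is a smaller stated number of children with full five-year data.

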9.2.2 Subject Enrollment

Subject recruitment will continue for 10 years, even if the expected sample size of 75 exposed pregnancies is reached at an earlier time point. If after 10 years the minimum sample size of 75/150 is not reached, enrollment will cease with the FDA's agreement.

Spontaneous referrals from MotherToBaby/OTIS member services and sites will be a source of recruitment for the Registry. MotherToBaby/OTIS Pregnancy Studies have utilized repeated direct mailing campaigns to provide information to health care

professionals who are likely to treat women with the underlying conditions of interest, and this strategy will be continued with the Registry. Registry staff will participate in scientific meetings of professional organizations to initiate and maintain relationships that have been established with referring physicians. In addition, members of the Advisory Board will be asked to promote recruitment among colleagues. The existing Toll Free number for North American callers currently being utilized by all MotherToBaby Pregnancy Studies [contact]) will be maintained and **has been** included in the product label for evolocumab.

The existing MotherToBaby/OTIS Pregnancy Studies contact and referral information is available on the web site and multiple methods are used to increase awareness through the website, social media, and print advertising. The FDA website lists the MotherToBaby/OTIS Pregnancy Studies including this Registry. The study **is** also listed on ClinicalTrials.gov. Additional venues for publicizing the Registry include advocacy groups and patient support networks for FH, and others such as Patients Like Me, BabyCenter.com, pharmacy groups, and professional practice organizations.

9.2.2.1 Subject Initiated Enrollment

Pregnant women can become enrolled into the study upon contacting the Registry at which time their eligibility will be evaluated. Pregnant women who contact the Registry and who do not meet the eligibility criteria for the cohort (cohort 1), but have had pregnancy exposure to evolocumab, will be consented, interviewed, medical records requested, and the outcome examination will be performed using the same protocol as cohort-eligible subjects. These subjects will not be included in the primary analysis for the cohort study, but will be included in the Evolocumab-Exposed Case Series (cohort 4). Collection of exposure and outcome information will follow the same time schedule to the extent this can be achieved as set forth in [Table 1](#). Subjects enrolled in the Evolocumab-Exposed Case Series will not be asked to participate in neurobehavioral testing.

9.2.2.2 Health Care Provider Initiated Enrollment

If the Registry is initially contacted by the health care provider he or she will be asked to have the subject contact the Registry to learn more about the study, and consent to participate if desired. The MotherToBaby service fax referral form (see [Appendix A, Form 01.A. MotherToBaby Service Fax Referral](#)) or the online physician referral form (<http://mothertobaby.org/healthcare-professional-referral-form/>) can be utilized for health care provider initiated referrals.

9.2.2.3 Other Sources of Subjects

- Amgen will provide the Registry with the number of reports of pregnancy exposures to evolocumab from the US or Canada received through safety surveillance processes or studies in order to assist with evaluating potential for recruitment; Amgen will encourage exposed women or their Health Care Providers to contact the Registry directly. Amgen may also provide information about the Registry at appropriate professional and advocacy meetings and facilitate awareness among prescribers through Medical Science Liaisons.
- Relevant reports from the published literature will be included in the Registry Annual Interim Reports and reviewed by the Scientific Advisory Board.
- If other data sources (unpublished) on fetal, infant, or childhood outcomes following maternal exposure to evolocumab during pregnancy are available, they may be included in the Appendices to the Registry Annual Interim Reports.

9.2.3 Subject Eligibility

9.2.3.1 Inclusion Criteria

(1) Specific Evolocumab-Exposed Cohort

- Qualified subjects will be currently pregnant women (maternal report validated by medical records) diagnosed with ASCVD, or hypercholesterolemia associated with FH who have been exposed to evolocumab for any number of days, at any dose, and at any time from the first day of the LMP up to and including the end of pregnancy. If the date of the LMP is unclear, or if a first-trimester ultrasound has been done and the estimated date of conception is more than 1 week discrepant from the menstrual period calculation, the first-trimester ultrasound-derived date will be used to calculate a date for LMP and conception.
- Qualified subjects will agree to the conditions and requirements of the study including the interview schedule, release of medical records, the physical examination of live born infants, and 5 years of follow-up.

(2) Comparison Group I

- Qualified subjects will be currently pregnant women (maternal report validated by medical records) diagnosed with ASCVD, or hypercholesterolemia associated with FH but who were not exposed to evolocumab during pregnancy or any time within 90 days prior to the first day of the LMP.
- Qualified subjects will agree to the conditions and requirements of the study including the interview schedule, release of medical records, the physical examination of live born infants, and 5 years of follow-up.

(3) Comparison Group II

- Qualified subjects will be currently pregnant women not diagnosed with ASCVD, or hypercholesterolemia associated with FH, who have not been exposed to evolocumab during pregnancy or any time within 90 days prior to the first day of the LMP, and who have no exposure to any known human teratogens as determined by the OTIS Research Center.
- Qualified subjects will agree to the conditions and requirements of the study including the interview schedule, release of medical records, the physical examination of live born infants, and 5 years of follow-up.

(4) General Evolocumab-Exposed Case Series

- Qualified subjects will be women with exposure to evolocumab during pregnancy who do not meet the criteria for the Specific Evolocumab-Exposed cohort for reasons including (but not limited to): they do not have ASCVD, or hypercholesterolemia associated with FH (off-label use), they were exposed to evolocumab but the pregnancy has already completed, they enrolled in the cohort study with a previous pregnancy, or they already have a prenatal diagnosis of a major **structural** birth defect.

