9.2.3.2 Exclusion Criteria

(1) Specific Evolocumab-Exposed Cohort

- Women who first contact the Registry after prenatal diagnosis of a major structural **birth** defect
- Women who were exposed to a different PCSK9 inhibitor during their current pregnancy or at any time within 5 half-lives prior to the first day of the LMP
- Women who have enrolled in this Registry with a previous pregnancy

(2) Comparison Group I

- Women who first contact the Registry after prenatal diagnosis of a major structural **birth** defect
- Women who have enrolled in this Registry with a previous pregnancy
- Women who were exposed to **any** PCSK9 inhibitor during their current pregnancy or at any time within 5 half-lives prior to the first day of the LMP

(3) Comparison Group II

- Women who first contact the Registry after prenatal diagnosis of a major structural **birth** defect
- Women who were exposed to any PCSK9 inhibitor during their current pregnancy or at any time within 5 half-lives prior to the first day of the LMP
- Women who have enrolled in this Registry with a previous pregnancy

(4) General Evolocumab-Exposed Case Series

- None

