9.3 Variables

9.3.1 Exposure Assessment

The period defining exposure to evolocumab during pregnancy will be any number of days, at any dose, and at any time from the first day of the LMP up to and including the end of pregnancy. Pregnancy will be assessed via maternal report validated by medical records. If the date of the LMP is unclear, or if a first-trimester ultrasound has been done and the estimated date of conception is more than 1 week discrepant from the menstrual period calculation, the first-trimester ultrasound-derived date will be used to calculate a date for LMP and conception.

The period defining non-exposure to evolocumab during pregnancy will be any time within 90 days prior to the first day of the LMP.

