9.4.2 Interim Interviews

Following the initial intake interview, **subjects** will be sent a pregnancy diary in which they will be asked to record any additional exposures or events as the pregnancy progresses (see [Appendix A](#), 03.D. Patient Exposure Diary), **as well as the obstetric medical record release form.**

A subject may have 1 to 3 interviews during pregnancy, with a minimum of 4 weeks between interviews. If a subject enrolls at 18 weeks, the 20-week interview will be scheduled at 22 weeks. If a subject enrolls between 19 weeks and < 30 weeks, the next scheduled interview will be at 32 weeks. If a subject enrolls at 30 weeks, the 32-week interview will be scheduled at 34 weeks. If a subject enrolls after 30 weeks, no additional interviews will be scheduled during pregnancy (see [Table 1](#), and [Appendix A](#), 02.C. Exposure Interview Form and 02.F. Outcome Delivery and Birth Interview Form). The purpose of these interviews will be to update records of pregnancy exposures and results of prenatal tests, to remind women to maintain the exposure diary, to update phone number and address information, and to determine if the pregnancy has ended prior to the expected due date.

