9.7.2.4.1 Description of Study Enrollment

Outcome	Analysis Subset
Major Structural Birth Defect Among Live Births	All pregnancies ending in at least 1 live born infant
Major Structural Birth Defects Among All Pregnancies Excluding Lost to Follow-Up	All pregnancies excluding lost to follow-up
Spontaneous Abortion	Pregnancies enrolled prior to 20 weeks' gestation
Stillbirth	Pregnancies enrolled excluding lost to follow-up
Preterm Delivery	Pregnancies enrolled prior to 37 completed weeks' gestation, excluding pregnancies ending in twin or higher order multiple births
Minor Structural Birth Defects	Live born infants who have received the dysmorphology examination
Small for Gestational Age Infants	Live born infants excluding twin or higher order multiple births
Breastfeeding	Pregnancies ending in at least 1 live born infant
Postnatal Growth	Live born infants followed up to 1 year postpartum, excluding twin or higher order multiple births
Serious or Opportunistic Infections	Live born infants followed up to 1 year postpartum
Immune Function	Live born infants who received the tetanus titer testing
Response to vaccines	Live born infants who received at least one vaccine
Neurodevelopment	Live born infants for whom developmental screening questionnaires were completed or face-to-face testing was completed

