9.7.2.5.2 Secondary Analysis

The following will comprise the secondary analyses:

1. Comparison of all secondary outcomes between the Specific Evolocumab-Exposed cohort and Comparison Group I
2. Comparison of the primary and all secondary outcomes between the Specific Evolocumab-Exposed cohort and Comparison Group II

The comparison of the prevalence of the total proportion of major structural **birth** defects between the Specific Evolocumab-Exposed cohort and Comparison Group II will be among all live births and, separately, among all pregnancies excluding those lost to follow-up. The comparison of the prevalence of ≥ 3 minor malformations between the Specific Evolocumab-Exposed cohort and each of the 2 comparison groups will be among children who receive the dysmorphological examination. The comparison of IgG-tetanus antibody status (test negative or indeterminate vs test positive) by group (Exposed, Comparison Group I, Comparison Group II) among those in the biological sample sub-study.

In each cohort we will separately calculate the proportion of all pregnancies ending in live birth, spontaneous abortion, stillbirth, elective termination, and lost to follow-up; crude comparisons will be made between cohorts.

The evaluation for a pattern of minor structural **birth** defects will be conducted using the following steps:

1. A comparison among groups of the proportion of infants with any 3 or more minor structural **birth** defects will be made without regard to pattern
2. Among infants with 3 or more minor **structural birth** defects, the Evolocumab-Exposed group will be examined for evidence of a specific pattern of 3 or more defects in any 2 or more children. If such a pattern is identified, Comparison Groups I and II will be evaluated for any evidence of the same pattern.

In each cohort among all live born infants we will separately calculate the proportion of premature delivery, small for gestational age on weight, length or head circumference, and rates of serious infections, hospitalizations, adverse vaccine reactions, and adverse neurodevelopmental outcomes; crude comparisons will be made between cohorts.

Mean birth weight, length and head circumference for full-term live born infants will be compared between cohorts. Postnatal growth parameters will be compared using the proportion of infants ≤ 10 th centile for sex and age with respect to weight, height, or head circumference.

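### Exposure is classified over the whole pregnancy, so a woman who starts evolocumab after enrolment can bring event-free weeks to the exposed side of the spontaneous abortion comparison

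*Protocol*

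**What the plan says.** Protocol 9.2.3.1 admits to the Specific Evolocumab-Exposed cohort women with the qualifying diagnosis who used evolocumab "at any time from the first day of the LMP up to and including the end of pregnancy". Section 9.3.1 repeats the window: "The period defining exposure to evolocumab during pregnancy will be any number of days, at any dose". Comparison Group I takes women with the same diagnoses "but who were not exposed to evolocumab during pregnancy or any time within 90 days prior to the first day of the LMP". Under 9.2.3.2, comparison women are excluded for exposure to any "PCSK9 inhibitor during their current pregnancy or at any time within 5 half-lives prior to the first day of the LMP", and the exposed cohort excludes "Women who were exposed to a different PCSK9 inhibitor during their current pregnancy". None of these rules names enrolment as the point at which status is fixed.

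Section 9.5 expects enrolment at 7-10 weeks on average. Interim interviews follow at 20-22 and 32-34 weeks, and 9.4.2 gives their aim: "The purpose of these interviews will be to update records of pregnancy exposures and results of prenatal tests".

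In 9.7.2.4.1 the spontaneous abortion subset is "Pregnancies enrolled prior to 20 weeks' gestation", with no condition on when exposure began. Section 9.3.2.2.1 ends that outcome at 19 completed weeks. For pregnancy outcomes, 9.7.2.5.2 says that "crude comparisons will be made between cohorts"; adjusted estimates by Cox, logistic or linear regression may follow, without mention of time-dependent exposure.

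**The concern.** Take a Group I woman enrolled at 9 weeks who starts evolocumab at 24 weeks. She now fails the Group I criterion and satisfies the exposed one. She was enrolled before 20 weeks, so she enters the spontaneous abortion table as exposed, although her first dose came after the last week in which she could have had that outcome. Had she miscarried at 12 weeks, she would have counted as an unexposed loss. This is immortal time: only women whose pregnancies continue can become late starters.

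Removing her from Group I without moving her does not help, because the women removed are all survivors and the Group I loss rate rises.

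Stillbirth and preterm delivery are affected in the same direction, by an amount that depends on the start week. In a safety registry the consequence is that a real increase in loss could be understated.

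The eligibility rules carry a related problem. If an exposed woman who later takes another PCSK9 inhibitor is excluded, or a Group II woman is dropped for a later teratogen, those exclusions also fall only on pregnancies that lasted long enough.

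**Working it through.** **Inputs.** From 9.5 and Table 3: 71 exposed and 142 comparison pregnancies; combined spontaneous abortion/stillbirth risk 10%; target RR 2.5; two-tailed alpha 0.05. Assumed, because the protocol gives no figure: the share f of exposed women who start after enrolment, and when they start.

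**The plan's own figure.** Table 3 states 88% power for this row. With 25% against 10% at 71 and 142, a two-sided pooled normal calculation gives 80.1% and Fisher's exact test 77.6%. A one-sided calculation gives 87.1%. The stated figure is therefore not reproduced under the stated two-tailed test. That is a separate matter; about 80% is the reference used below.

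**Spontaneous abortion, no true effect, 7 late starters.** Let r be the risk in every woman from enrolment, with 64 women exposed before enrolment and 149 enrolled in Group I, of whom 7 start after 19 weeks.

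- Exposed: 64r/71. With r = 10%, 6.4/71 = 9.0%.
- Group I after the 7 leave: 149r/142. With r = 10%, 14.9/142 = 10.5%.
- RR = (64/71) × (142/149) = 0.901 × 0.953 = 0.86.

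The risk r cancels, so it does not matter that Table 3's 10% combines abortion and stillbirth.

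- If the 7 are only dropped from Group I: (6.4/64)/(14.9/142) = 142/149 = 0.95.
- If status is fixed at enrolment: (6.4/64)/(14.9/149) = 1.00.

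**Other shares.** RR = (1 − f) × 142/(142 + 71f).

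| f | Women (71f) | RR read when the truth is 1.0 |
|---|---|---|
| 0% | 0 | 1.00 |
| 5% | 3.6 | 0.93 |
| 10% | 7.1 | 0.86 |
| 20% | 14.2 | 0.73 |
| 30% | 21.3 | 0.61 |

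**Masking of harm.** Leaving the comparison rate unchanged, a true RR of 2.5 reads 2.5 × (1 − f): 2.25 at f = 10% and 2.00 at f = 20%. Using 10% as the baseline, two-sided power falls from about 80% to 68% and 52%.

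**All losses combined.** Late starters can still have a stillbirth, so the shift is smaller for earlier starts. With 10% risk spread from week 8.5 to week 40, a hazard halving every 3 or 6 weeks, and start weeks 12 to 28 (all assumed), a true RR of 1.0 reads 0.93-0.98 at f = 5%, 0.86-0.95 at 10%, 0.73-0.90 at 20% and 0.61-0.86 at 30%. In the same model, splitting each woman's time at first dose returns the true RR.

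**The case against.** The strongest reply is that reassignment is inferred. No section says that a woman changes group or is removed after enrolment. Eligibility is evaluated on contact with the Registry (9.2.2.1), and the criteria use the past tense for women who are currently pregnant. This stands as far as it goes: a reader might infer that the protocol orders late starters into the exposed cohort, and it does not. But an exposure window that runs to the end of pregnancy, and a Group I criterion covering the whole pregnancy, do not fit a status frozen at enrolment. Section 9.3.1 adds to the doubt by describing non-exposure only through the 90 days before LMP.

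A reader might also take 9.7.2.6 as proof that such women are expected. It speaks of second- and third-trimester exposures. That also covers women who continue from the first trimester and women first exposed later but before enrolling, so it says nothing about f.

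Section 9.7.2.6.1 plans subgroups by timing and length of exposure as feasible, and a Cox model is named. Neither clearly removes the problem: a Cox model with cohort as a fixed covariate keeps it. Time-dependent coding could be left to an analysis plan, but the cohort definitions that such a plan would inherit are set here.

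Finally, the shift is small beside sampling error. With 7/71 against 14/142, the standard error of log RR is √(1/7 − 1/71 + 1/14 − 1/142) = 0.44, so the 95% interval around 1.0 is about 0.42 to 2.37. That limits the practical weight of the point but does not excuse a bias of known direction that can be avoided.

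**Conclusion.** The point holds as a defect in how exposure is classified for outcomes tied to gestational time. For spontaneous abortion, late starters pull the RR down: to about 0.86 from 1.0 if 7 of 71 exposed women are first dosed after 19 weeks and come from Group I, and not at all if there are none. The number 7 is an assumption; the true share is undocumented and may be small, since 9.7.2.6 intends first-trimester exposure for the primary endpoint.

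Three stronger readings are not supported:

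- That evolocumab will look protective overall. The size rests on an unknown share, a true increase would be understated rather than reversed in the cases computed, and excluding exposed women who switch to another PCSK9 inhibitor would push the other way.
- That 0.86 applies to all losses. It holds only for spontaneous abortion, because late starters remain at risk of stillbirth.
- That the primary birth-defect comparison is affected. The calculation does not bear on it.

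This should be corrected, but it does not threaten the study's main result.

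**What to change.** 1. In 9.7.2.4.1 and 9.7.2.5.2, state that for spontaneous abortion, stillbirth and preterm delivery a woman contributes unexposed time from enrolment until her first dose and exposed time afterwards. The Cox model already named serves, with time-dependent exposure and entry at enrolment.
2. In the crude spontaneous abortion and preterm tables, classify women by exposure status at enrolment. In no case count as exposed for spontaneous abortion a woman first dosed at or after 19 completed weeks. A rule that accepts any first dose before 37 weeks would not do for preterm delivery: a woman enrolled at 9 weeks and starting at 30 would still bring 21 event-free weeks.
3. In 9.2.3, state that the PCSK9-inhibitor and teratogen criteria are applied at enrolment. Flag later exposures and add a sensitivity analysis that censors at the switch.
4. Keep any-time-in-pregnancy exposure for infant immune, growth and neurodevelopmental outcomes. Fixing groups at enrolment there would count infants exposed late in utero as unexposed, although 9.4.5.2 treats exposure beyond the first trimester as relevant to brain development.

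The cost is wording, slightly fewer exposed women in the spontaneous abortion comparison, and a little more analysis work. Exposures are already updated at each interview, so no new contact with subjects is needed.
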